Indicator of sexually active denovo dyspareunia**	PISQ-IR	Binary	surgery through 3 years	At each timepoint among women who were sexually active (PISQ-IR Q1: 1=yes) at baseline and at the timepoint's corresponding attended post-operative visit, based on the response to the PISQ-IR question Q11 "How often do you feel pain during sexual intercourse? " at baseline and the timepoint's corresponding attended post-operative visit, the indicator is defined as follows:
				1 = Yes, if a response of 1=never or 2=rarely is reported at baseline and a response of 3=sometimes, 4=usually, or 5=always is

				reported at the timepoint's corresponding attended post-operative visit 0 = No, else if there is a non-missing response reported at baseline and at the timepoint's corresponding attended post-operative visit . = Missing, otherwise
Indicator of not sexually active denovo dyspareunia**	PISQ-IR	Binary	surgery through 3 years	At each timepoint among women who were not sexually active (PISQ-IR Q1: 2=no) at baseline and at the timepoint's corresponding attended post-operative visit, based on the response to the PISQ-IR question Q2e asking if pain is a reason for not being sexually active at baseline and the timepoint's corresponding attended post-operative visit, the indicator is defined as follows:
				1 = Yes, if a response of 3=somewhat disagree or 4=strongly disagree is reported at baseline and a response of 1=strongly agree or 2=somewhat agree is reported at the timepoint's corresponding attended post- operative visit
				0 = No, else if there is a non-missing response reported at baseline and at the timepoint's corresponding attended post-operative visit
				. = Missing, otherwise
Indicator of dyspareunia	CRF-13, CRF-96	Binary	surgery through 3 years	Through the timepoint of follow-up, based on the Adverse Event Log (CRF-96) or specific complications as reported on the coordinator follow-up CRF-13 collected in 6-month intervals through 3 years, the indicator is defined as follows:

				1 = Yes, if denovo dyspareunia, worsening dyspareunia, or dyspareunia preventing intercourse is reported as evident (i.e. response of "AE", "SAE") on any of the complication tables as described above or "Dyspareunia" in the term reported in the AE log.
				0 = No, else if subject attended at least one post- operative visit 6 months or after and complication(s) of interest specified above are reported as "Not Evident" across all attended post-operative visits. Subjects with missing responses are included as long as the subject has at least one "Not Evident" response (assuming low missing response rate among attended visits).
				
 
. = Missing, otherwise
 
*Note: Prior to and upon database lock, any dyspareunia events identified by the MedDRA coded preferred term "dyspareunia" ) with start date after surgery collected ONLY on the AE log and not reported on any of the complications tables will be assessed, and if any, included in this definition at the discretion of the principal investigator.
 

Indicator of new or worsening voiding dysfunction	CRF-12, CRF-13, CRF-96	Binary	surgery through 3 years	Through the timepoint of follow-up, based on the Adverse Event Log (CRF-96) or specific complications as reported on the masked post-operative CRF-12 and coordinator follow-up CRF-13 collected at 6-weeks and

in 6-month intervals through 3 years, the indicat defined as follows:	or is
1 = Yes, if new or worsening difficulty em bladder is reported as evident (i.e. of "AE", "SAE") on any of the com tables as described above or "Urina Retention" in the term reported in t log Masked review identified free other specify complication fields co "incomplete bladder emptying", retention " (case insensitive) on any complication tables as described ab CRF-12 collected at 6-weeks and in intervals through 3 years and 1-yea thereafter.	response nplication ary the AE text ontaining "urinary y of the pove or on n 6-month
0 = No, else if subject attended at least one p operative visit 6 weeks or after and complication(s) of interest specified are reported as "Not Evident" across attended post-operative visits. Subj missing responses are included as le subject has at least one "Not Eviden response (assuming low missing response (assuming low missing response).	d above ss all ects with ong as the nt"
. = Missing, otherwise	
*Note: Prior to and upon database lock, any void dysfunction events identified by the MedDRA co preferred term "urinary retention" collected ONI AE log with start date after surgery and not repo any of the complications tables will be assessed,	oded LY on the orted on

				any, included in this definition at the discretion of the principal investigator.
Regret with Decision Scale (DRS-PFD)	CRF-25	Continuous	12-, 24-, and 36-months	5-item questionnaire with a 5-point response scale. Scoring consists of reversing the scores of the 2 negatively phrased items, then taking the mean of the 5 items (range, 1-5).
Satisfaction with Decision Scale (SDS- PFD)	CRF-25	Continuous	12-, 24-, and 36-months	6-item questionnaire with a 5-point response scale. Scoring consists of taking the mean of the 6 items (range, 1-5).

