sexual partner (i.e. Q12: 1=yes) sum the scores for
questions Q7, Q8a-c, Q9, Q10, Q11, Q13, Q14a-b, Q15,
Q16, Q17, Q18, Q19a-c, Q20a-d using reverse scores for
Q8b-c, Q9, Q11, Q14a-b, Q16, Q17, Q18, and Q19a-c
(Q7, Q8a-c, Q9, Q11: 1=never,, 5=[almost] always;
Q10: 1=much less intense,, 5=much more intense; Q13:
1=all of the time,, 4=hardly ever/rarely; Q14a-b:
1=very positive,, 4=very negative; Q15: 1=never,,
5=always; Q16: 1=daily,,5=never; Q17: 1=very high,
, 5=very low or none at all; Q18: 1=not at all,, 4=a
lot; Q19a-c: 1=satisfied,, 5=dissatisfied; Q20a-d:
1=strongly agree,, 4=strongly disagree). If there are
more than 10 missing responses, then a total score is not
calculated. Similarly, for subjects without a sexual partner
(i.e. Q12: 2=no) sum the scores as described above
excluding Q13 and Q14a-b from the sum as these
questions are not collected among subjects without a
sexual partner. If there are more than 9 missing responses,
then a total score is not calculated. To handle missing
values, the final score is obtained by dividing the sum by
the number of items answered. The outcome will then be
computed as the difference in score at each timepoint's
corresponding attended post-operative visit and the score
at baseline. If data for the assessment are missing at a
timepoint's corresponding attended post-operative visit,
the outcome variable will be coded as missing. Scores
should only be calculated for participants that are
sexually active.
bonduny uotivo.

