Change from baseline in Functional Activity Assessment Scale (FAS) overall score	AAS	Continuous	6-, 12-, 24-, 36-, 48, 60- months	The Functional Activities Assessment Scale (FAS) score will be computed at baseline and at each timepoint's corresponding attended post-operative visit during which assessments are administered and collected using standard scoring algorithms (McCarthy 2005). Specifically, sum the scores for questions Q1,, Q13 (1=no difficult,, 5=not able to do it; responses of 6=did not do it for other reasons will not be included in the sum). If there are more than 6 missing responses, then a total score is not calculated. To handle missing values, the raw score is obtained by dividing the sum by the number of items answered. The final score is obtained by scaling the raw score to range from 0 to 100 using the following formula: (65 – raw score)/52 x 100 Note: 65 is the maximum raw score, and 52 is the range of possible scores (65-13=52). The outcome will then be computed as the difference in score at each timepoint's corresponding attended post- operative visit and the score at baseline. If data for the assessment are missing at a timepoint's corresponding attended post-operative visit, the outcome variable will be coded as missing.
Change from baseline in SF-12 physical component PCS Subscale	SF-12	Continuous	6-, 12-, 24-, 36-, 48, 60- months	At baseline and at each timepoint, based on physical component items as reported on the SF-12 at the timepoint's corresponding attended post-operative visit, the scoring of the physical component subscale is defined in Attachment 1 .

				The outcome will then be computed as the difference in score at each timepoint's corresponding attended post- operative visit and the score at baseline. If data for the assessment are missing at a timepoint's corresponding attended post-operative visit, the outcome variable will be coded as missing.
Change from baseline in SF-12 mental component MCS Subscale	SF-12	Continuous	6-, 12-, 24-, 36-, 48, 60- months	At baseline and at each timepoint, based on mental component items as reported on the SF-12 at the timepoint's corresponding attended post-operative visit, the scoring of the mental component subscale is defined in Attachment 1 .

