## 9.5 Secondary Efficacy Analysis Methods

### **9.5.1** Secondary Efficacy Outcomes

All secondary anatomical and functional efficacy outcomes are collected longitudinally across the study. All analyses for secondary outcomes are considered to be descriptive rather than inferential, so p-values will be interpreted as measures of evidence of descriptive differences in the treatment arms, not formal inferences.

For all secondary outcomes, point estimates and 95% confidence intervals for pairwise comparisons between each of the mesh repairs versus the native tissue repair as well as between the two mesh repairs will be obtained along with a p-value for the overall test assessing if any of the treatment effects are different. Treatment groups will be compared in the MITT population for all secondary efficacy outcomes.

Unless otherwise specified, all other secondary efficacy outcomes collected across multiple visits, analyses will include data only collected through 3 years (visits occurring after 3 years are excluded) using appropriate adjusted repeated measures models that account for subject correlations across visits. If the data corresponding to a secondary efficacy outcome is also collected at baseline prior to surgical intervention, these outcomes will be analyzed as change from baseline. Models will be adjusted for randomized surgical intervention, time in months as intended by the visit schedule, intervention by time interaction, baseline value, pooled site and age category consistent with study randomization design.

Treatment groups will be compared for any secondary efficacy outcomes evaluated in an aggregate fashion (e.g. proportion of participants with an event occurrence through 3 years), using a chi-square test or Fishers exact test for rare events. Additional details are provided in the specific sections below.

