# 15 ATTACHMENTS

## 15.1 Attachment 1: Scoring of the SF-12 PCS and MCS Subscales

The scoring of the SF-12 QOL assessment was found at

https://drhays.dgsom.ucla.edu/files/view/docs/programs-utilities/sf12v1\_short.sas.txt. This attachment provides a summary of the calculations for both the Physical Component Summary (PCS) and Mental Component Summary (MCS) subscales of the SF-12.

The SF-12 is comprised of 12 questions. Q1, Q8, and Q12 use five-number scales; Q4 through Q7 use yes/no scales; and Q 2 and Q3 have three-number scales; and Q9 through Q11 use sixnumber scales. For Q1 and Q8, values are assigned to each response as follows: 100=excellent, 75=very good, 50=good, 25=fair, 0=poor. For Q12, values are assigned to each response as follows: 100=none of the time, 75=a little of the time, 50=some of the time, 25=most of the time, 0=all of the time. Q2 and Q3 receive values as follows: 0=yes, limited a lot; 50=yes, limited a little; 100=no, not limited at all. For Q4-Q7, values are assigned as follows: 0=yes and 100=no. For Q9 and Q10, values are assigned to each response as follows: 100=all of the time, 80=most of the time, 60=a good bit of the time, 40=some of the time, 20=a little of the time, 0=none of the time. For Q11, values are assigned to each response as follows: 0=all of the time, 20=most of the time, 40=a good bit of the time, 60=some of the time, 80=a little of the time, 100=none of the time.

With values assigned to each question, the raw PCS and MCS scores are then calculated as a weighted sum based on the assigned value for each question. The weights are provided in Table A-1 and Table A-2. The PCS and MCS subscales are then calculated by multiplying these sums by 10 and adding a constant to each raw score (PCS=56.57706, MCS=60.75781).

Question	Assigned Value						
Number	0	20-25	40	50	60	75-80	100

 Table A-1. Sum Weights for Question Values – PCS

Version 1.0, 8/17/2022; Page 88

	1			1			
1	-8.37399	-5.56461		-3.02396		-1.31872	0
2	-7.23216			-3.45555			0
3	-6.24397			-2.73557			0
4	-4.61617						0
5	-5.51747						0
6	3.04365						0
7	2.32091						0
8	-11.25544	-8.38063		-6.50522		-3.80130	0
9	3.46638	2.90426	2.37241		1.36689	0.66514	0
10	-2.44706	-2.02168	-1.61850		-1.14387	-0.42251	0
11	4.61446	3.41593	2.34247		1.28044	0.41188	0
12	-0.33682	-0.94342		-0.18043		0.11038	0

 Table A-2. Sum Weights for Question Values – MCS

Question Number	Assigned Value									
	0	20-25	40	50	60	75-80	100			

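### The FAS and SF-12 scoring rules in the SAP do not give scores on the intended scales: the FAS formula expects a 13–65 total but receives a 1–5 mean, and the SF-12 weighted sums are multiplied by 10

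*SAP*

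**What the plan says.** **FAS (SAP 9.3, Efficacy Variables).** Thirteen items are scored 1 to 5. A sixth answer code exists, and "responses of 6=did not do it for other reasons will not be included in the sum". A form with more than 6 missing items gets no score. For missing values, "the raw score is obtained by dividing the sum by the number of items answered". The raw score is then rescaled by (65 − raw)/52 × 100, with a stated result of 0 to 100. The entry explains its constants: "Note: 65 is the maximum raw score, and 52 is the range of possible scores (65-13=52".

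**SF-12 (SAP 15.1, Attachment 1).** Each answer is given a weight from Table A-1 (PCS) or Table A-2 (MCS), and the weights are summed to form the raw score. Then: "The PCS and MCS subscales are then calculated by multiplying these sums by 10 and adding a constant to each raw score". The constants are 56.57706 (PCS) and 60.75781 (MCS). No range is stated for either scale. The attachment is a summary and points to an external scoring program.

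**Use.** SAP 3.2 lists both among the outcomes for the primary manuscript. Both are analysed as change from baseline (SAP 9.3 and 9.5.1). On their status, SAP 9.5.1 says: "All analyses for secondary outcomes are considered to be descriptive rather than inferential". The Version 2 updates in SAP section 12 do not touch scoring.

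**The concern.** The FAS entry contradicts itself. A maximum of 65 and a range of 52 fit only a 13-item total, yet the quantity entered is an item mean. It is also unclear which forms are divided. The PISQ-IR average score in the same table has a nearly identical sentence ("values, the final score is obtained by dividing the sum by" the number of items answered). There it must apply to all forms, and it does no harm because no rescaling follows. The FAS could be read the same way, or as dividing only forms with gaps.

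For the SF-12, the tabled weights already span about 60 to 66 points and are on the same scale as the constants. A further factor of 10 has no visible purpose.

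For descriptive outcomes, the estimate and its interval are the result. If the code follows the text, the reported arm differences in function and quality of life would be in the wrong units and could not be compared with other trials. Under one reading of the FAS rule, the comparison between arms would also be distorted.

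**Working it through.** **FAS.** Inputs from SAP 9.3: 13 items, answers 1 to 5, f(raw) = (65 − raw)/52 × 100.

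The plan's own 0 to 100 range is reproduced only when raw is the total:

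| All 13 answers equal to | f(total) | f(mean) |
|---|---|---|
| 1 | f(13) = 100.0 | f(1) = 123.1 |
| 2 | f(26) = 75.0 | f(2) = 121.2 |
| 3 | f(39) = 50.0 | f(3) = 119.2 |
| 5 | f(65) = 0.0 | f(5) = 115.4 |

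*Reading 1, every form divided.* All scores lie between 115.4 and 123.1. The scale is 7.69 points wide instead of 100, a ratio of 13. Moving from all 3s to all 2s gives f(2) − f(3) = +1.9 instead of f(26) − f(39) = +25.0.

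*Reading 2, only forms with unanswered items divided.* Answers of 2 throughout score 75.0 on a complete form and 121.2 with one item blank. The same true change of +25.0 becomes:
- f(2) − f(39) = +71.2 if the blank is only at follow-up;
- f(26) − f(3) = −44.2 if the blank is only at baseline.

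Suppose answers are near 2 and baseline completeness is equal across arms. Each 10-percentage-point arm difference in incomplete follow-up forms then shifts the unadjusted mean difference by 0.10 × (121.15 − 75.0) = 4.6 points.

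*Dropping the division altogether* does not work either. With 7 items answered, the plain sum runs from 7 to 35, so scores run from f(35) = 57.7 to f(7) = 111.5.

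*Prorated total, raw = 13 × (sum / items answered).* Item means of 1, 3 and 5 give raw values of 13, 39 and 65, and scores of 100, 50 and 0. Complete forms keep their plain total. Answer code 6 still needs a rule. Take ten items answered 2 and three coded 6, so the sum is 20. If code 6 is missing, raw = 13 × 20/10 = 26 and the score is 75.0. If those items count as answered, raw = 13 × 20/13 = 20 and the score is f(20) = 86.5.

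**SF-12.** Inputs are the weights in Tables A-1 and A-2 and the two constants. Taking the lowest and highest weight for each item gives sums of −46.63 to 13.56 (PCS) and −54.87 to 11.53 (MCS).

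| | Sum + constant | 10 × sum + constant |
|---|---|---|
| PCS limits | 9.9 to 70.1 | −409.7 to 192.1 |
| MCS limits | 5.9 to 72.3 | −487.9 to 176.0 |
| Middling respondent, PCS | 56.58 − 12.27 = 44.3 | 56.58 − 122.71 = −66.1 |
| Middling respondent, MCS | 60.76 − 6.61 = 54.1 | 60.76 − 66.10 = −5.3 |

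The middling respondent has assigned values Q1 = Q2 = Q3 = 50, Q4 to Q7 = 100, Q8 = 75, Q9 = Q10 = 60, Q11 = 80 and Q12 = 75. Moving Q8 alone from 50 to 75 changes PCS by −3.80130 − (−6.50522) = 2.7 without the factor and 27.0 with it.

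**The case against.** The strongest reply is that these are drafting slips. The FAS entry cites a published algorithm, sets a 0 to 100 target and states its constants, so the intended total can be recovered, and a range check would expose scores above 100. Nothing shows that the code follows the literal text. That is fair about intent, but the written rule cannot be run as it stands and nothing else in the SAP corrects it.

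The largest FAS distortions depend on reading 2, and the documents do not say how often forms are incomplete. Both points stand, and those figures should be read as conditional. Gaps are nevertheless built into the rule, which allows up to 6 missing items and an unscored answer code. Proration is likewise an inference from the stated constants and missing-item rule, and should be checked against the cited algorithm.

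For the SF-12, the SAP states no range and the cited program was not available. The case is therefore a strong inference from the size of the weights and constants, not a contradiction within the text. The limits in the table are bounds, not typical patients, and the middling MCS of −5.3 is only slightly negative. The middling PCS of −66.1 is harder to explain.

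Finally, SAP section 12 already reports post-hoc event counts, so analysis had begun. This makes the code check the practical priority.

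**Conclusion.** The point holds. The FAS half is established within the SAP: no response pattern reaches the declared range if the division applies to all forms, and two scales share one variable if it applies only to incomplete ones. The SF-12 half rests on the SAP's own tables and constants, subject to confirmation in the cited program.

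Under FAS reading 1 and for the SF-12, the error is a uniform rescaling. FAS changes are 1/13 of the intended size and SF-12 changes are 10 times it, while direction and p-values are unchanged. Under FAS reading 2, means, variances, tests and even the sign of an individual change can be wrong. The primary endpoint and the four formal hypothesis tests are untouched.

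A smaller, separate definitional gap lies in the same table. One PISQ-IR de novo dyspareunia indicator applies "At each timepoint among women who were sexually active (PISQ-IR Q1: 1=yes) at baseline and at the" visit, the other "At each timepoint among women who were not sexually active (PISQ-IR Q1: 2=no) at baseline and at the" visit. A woman whose status changes between the two has no value on either. The CRF-13/AE-log indicator can still count her, so the conclusion here does not depend on it.

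**What to change.** 1. **FAS (SAP 9.3).** For every form with no more than 6 missing items, define raw = 13 × (sum / items answered), then apply (65 − raw)/52 × 100. State whether answer code 6 counts as missing, both for the denominator and for the 6-item limit. Confirm against the algorithm the SAP cites.
2. **SF-12 (SAP 15.1).** Check the cited scoring program. If it agrees, delete the multiplication by 10, so that PCS = sum + 56.57706 and MCS = sum + 60.75781.
3. **Code.** Check both derivations in the analysis programs. Add range checks: 0 to 100 for the FAS, and the limits implied by Tables A-1 and A-2 for the SF-12. Rerun any affected tables. Record the correction as a dated SAP update.
4. **Optional.** Report by arm how many women active at baseline are inactive at the visit and give pain as a reason (PISQ-IR Q2e), beside the existing indicators and not merged with them.

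The cost is a few sentences of SAP text and a check of derivation code. All items are already collected.
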